# Integrating Animal-Assisted Therapy Into Trauma-Focused Cognitive-Behavioral Therapy for Maltreated Youth (TF-CBT+AAT) Protocol

## 1.0 Inclusion and Exclusion Criteria

### 1.1 Inclusion Criteria

#### Minor Patients

- Age 6-17 years (inclusive) with a participating consenting caregiver with legal standing to consent for the minor child (either biological parent or adoptive parent). All youth will be asked to provide assent.
- Sex: male or female
- Fluent in written and spoken English, as the assessment instruments are not available in translations and have not been validated for use with non-English speaking populations.
- An allegation of abuse or neglect investigated by law enforcement or child protective services.
- A raw score of  $\geq 39$  on the caregiver-report version of the UCLA PTSD Reaction Index completed by the caregiver upon presentation to the TLC Clinic or the Pinnacle Health Children's Resource Center (CRC).
- A full scale IQ score of  $\geq 80$  on the Kaufman Brief Intelligence Test (2nd ed.; KBIT-2)

#### Adult Caregiver

- Biological or adoptive parent of a child meeting inclusion criteria. Must consent to his/her own participation as well as the participation of the child.
- Self-identified as the primary caregiver (responsible for the day-to-day care of the child).
- Age  $\geq 18$  years
- Sex: male or female
- Fluent in written and spoken English. See rationale above regarding measures.

NOTE: Only youth were enrolled and only data pertaining to youth functioning was collected. However, given the importance of caregiver report for assessing these outcomes, inclusion and exclusion criteria related to the caregivers was included.

## 1.2 Exclusion Criteria

### Minor Patients

- Age <6 or >18 years
- 6-18 years of age and unwilling to give assent
- A diagnosed cognitive or intellectual deficit, or developmental delay
- An IQ score < 80 on the KBIT-2
- A reported fear of dogs, dog allergy, or prior history of aggression toward animals.

### Adult Caregiver

- Age < 18 years at the time of enrollment
- Caregiver inability to participate in treatment or to complete assessment measures due to cognitive, psychiatric, or other limitation.
- Suspected or known to have perpetrated a form of child maltreatment.
- A reported fear of dogs, dog allergy, or prior history of aggression toward animals

## 2.0 Recruitment Methods

### 2.1 Identification of subjects

Participants will be recruited through two mechanisms. First, children presenting for services at the Penn State Children's Hospital's Stine Foundation Transforming the Lives of Children (TLC) Clinic will be eligible for inclusion. The TLC Clinic exclusively serves maltreated children and, as a condition of admission, an investigated allegation of child maltreatment is required. Children meeting inclusion criteria following their initial assessment at the TLC Clinic will be offered participation in the trial.

Second, children presenting to the Pinnacle Health Children's Resource Center (CRC) for forensic interviews following allegations of maltreatment will be referred to the HMC research team. CRC involvement is limited to providing the attached recruitment letter to the parent of the child who may be eligible for this research.

NOTE: Only youth were enrolled and only data pertaining to youth functioning was collected. However, given the importance of caregiver report for assessing these outcomes, inclusion and exclusion criteria related to the caregivers was included. In addition, caregivers provided consent for the participation of the youth in the study.

## **2.2 Recruitment process**

Potential participants will be referred to study coordinators who will conduct a phone screen for eligibility related to the inclusion of the dogs, explain the study procedures and review inclusion/exclusion criteria. Pending meeting inclusion/exclusion criteria, those interested in participating will be scheduled an assessment session.

## **2.3 Recruitment materials**

The attached recruitment letter will be distributed to potential participants at the time they are identified as meeting initial eligibility at presentation to either the TLC Clinic or CRC.

## **2.4 Eligibility/screening of subjects**

Once participants are contacted by study coordinators, a brief screening questionnaire will be administered over the phone (see attached). Participants who agree to participate will be scheduled for the pre-treatment assessment session where the KBIT-2 and other study measures will be implemented. Final eligibility will be determined after this session.

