**(3) Emotion regulation** will be assessed in three ways. First, caregivers will complete the Emotion Regulation Checklist (ERC; Shields & Cicchetti, 1997) during the pre- and post-treatment assessments. Similarly, children will complete the self-report Emotion Regulation Index for Children and Adolescents (ERICA; MacDermott et al., 2010) during the pre- and post-assessments. Last, children's resting and stress reactivity respiratory sinus arrhythmia (RSA) will be assessed both pre- and post-treatment. RSA is assessed via an electrocardiogram (ECG) and is a well-established psychophysiological marker of emotion regulation (Beauchaine, 2015). RSA will be assessed with a UFI 3991/4 EIRS BioLog ambulatory physiological data recorder using disposable Ag/AgCl electrodes. Electrodes will be placed on the chest and abdomen to acquire inter-beat intervals. Placement of the electrodes will be facilitated by the research assistant conducting the assessment and the child's caregiver will be present during the application and later removal of the electrodes. The caregiver will not be present during the administration of the assessment procedures. To assess resting RSA, children will watch pre-selected television programs that are not emotionally-laden for 15 minutes. Stress reactivity will then be assessed using the Trier Social Stress Test (TSST; Buske-Kirschbaum et al., 1997; Kirschbaum et al., 1993). In addition, children will be shown a \$15 gift card to a toy or electronics store prior to beginning the TSST and told that they must achieve a satisfactory performance across the TSST tasks to earn the gift card. The gift card will be provided to all participants at the completion of the TSST. In both the resting and stressor paradigms, RSA will be sampled in 30 second epochs. [name], who will be blind to participant condition, will be responsible for editing the ECG files to remove artifacts and scoring the files using CardioEdit and CardioBatch software (Brain-Body Center, University of Illinois at Chicago, 2007). [name] is trained and certified by the developers in the use of this software. **(4) Youth perception of the caregiver** will be assessed at both the pre-treatment and post-treatment assessment sessions using the Security Scale, to determine whether participation in TF-CBT improved the youth's perception of their caregiver as a source of support. To examine potential caregiver-

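### The KBIT-2 shares a session with the social stress test and eligibility is settled only afterwards, so a child who fails the IQ cut can be put through the full battery for nothing

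*Combined protocol and SAP*

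**What the plan says.** **The criterion.** Section 1.1 requires a full-scale KBIT-2 score of at least 80. Section 1.2 lists the mirror exclusion, "An IQ score < 80 on the KBIT-2", and separately excludes "A diagnosed cognitive or intellectual deficit, or developmental delay".

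**When it is measured.** Section 2.4 books those who agree to take part for the pre-treatment session, "where the KBIT-2 and other study measures will be implemented. Final eligibility will be determined after this session". Consent is taken at the same visit (section 3.1.1.1).

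**What else happens at that visit.** Section 4.2 places the additional measures in the pre-treatment session. Under Measures, item (3), resting and stress-reactivity RSA are recorded before and after treatment. This means chest and abdominal electrodes and 15 minutes of resting recording, after which: "Stress reactivity will then be assessed using the Trier Social Stress Test". The caregiver is out of the room during these procedures. Children are shown a gift card and "told that they must achieve a satisfactory performance across the TSST tasks to earn the gift card"; in fact every child receives it at the end. The child UCLA, SDQ, SCARED, MFQ, ERC and ERICA are also pre-treatment measures.

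**The concern.** The IQ criterion can be checked only by giving the test, and the plan gives it in the same sitting as the most demanding procedure in the assessment. Because the eligibility decision is placed after the session, the most natural reading is that the whole battery is run first and the IQ cut applied afterwards.

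The children concerned have an investigated allegation of abuse or neglect and a caregiver-reported UCLA score of at least 39 (section 1.1). For a child who turns out to be below 80, the stress test brings no planned scientific return: the child is not eligible to be randomised, and Statistical methods (section 5.2) bases the analyses on data from randomised participants. What is at stake is research burden that a different order of testing would avoid.

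**Working it through.** **1. Can anything before the session catch a score below 80?**

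| Step | Where | Can it apply the IQ cut? |
|---|---|---|
| Record review | 3.1.2 | No. It serves preliminary eligibility and gives no KBIT-2 score. |
| TLC Clinic initial assessment | 2.1 | No. It speaks of children meeting the inclusion criteria, but 2.4 places the KBIT-2 later. |
| Phone screen | 2.2, 2.4 | No. It covers dog-related eligibility and a review of the criteria, with no IQ test. |
| Exclusion for cognitive deficit | 1.2 | Only where a deficit or delay is already diagnosed. |
| KBIT-2 | 2.4 | Yes, but in the same session as the other measures. |

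The group left exposed is children with no diagnosed deficit who score below 80.

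**2. Does any text set the order within the session or stop it early?** Sections 2.4 and 4.2 and the Measures text contain no statement that the KBIT-2 comes first, that it is scored before the other measures, or that the session ends on a score below 80. The only timing given is that final eligibility follows the session.

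**3. Does this touch the sample size?** The plan's own figure is a difference of about 5 points on pre-post UCLA change with 60 children in equal arms, SD 6.5, 80% power and alpha .05 (Sample size determination, also numbered 5.2). Taking the test as two-sided, with 30 per arm:

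- Normal approximation: 6.5 × (1.960 + 0.842) × √(2/30) = 4.70 points.
- t-test: 4.78 points.

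Both agree with the stated figure. The calculation concerns 60 allocated children, and neither the present timing nor an earlier KBIT-2 alters it.

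**4. How many children might be affected?** The documents give no IQ distribution and no screen-failure rate, so this is illustration only. Let f be the share of children reaching the session who score below 80, with no other losses. Randomising 60 requires 60/(1 − f) children to be assessed, so the number of ineligible children assessed is 60/(1 − f) − 60.

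| Assumed f | Children assessed | Ineligible children assessed |
|---|---|---|
| 3% | 60/0.97 = 61.9 | 1.9 |
| 5% | 60/0.95 = 63.2 | 3.2 |
| 9% | 60/0.91 = 65.9 | 5.9 |

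The 9% row corresponds to an unselected normal distribution with mean 100 and SD 15: Φ((80 − 100)/15) = Φ(−1.333) = 0.091. The 3 to 5% rows suppose that record review and the phone screen have already removed much of the lower tail. If the KBIT-2 were given and scored first, the number taken through the stress test would be close to zero in every row.

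**The case against.** The strongest reply is that the plan does not say a failing child must complete the stress test. It fixes no order, and staff could give the KBIT-2 first and stop. This stands as a limit on the point: a reader might infer that every ineligible child goes through the full battery, and the documents do not show that. They show that it is permitted, and that the stated timing of the decision points that way.

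A reader might also infer that children who fail the cut could be counted towards the 60 participants in section 5.1, leaving fewer randomised. The documents do not support this. Sample size determination describes the 60 as split equally across the two conditions, and Statistical methods refers to randomised participants. A child who is never allocated belongs to neither condition.

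Nor is there anything in the documents to show that children below the cut would find the stress-test tasks harder than others.

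On size, the reply is right that every count is assumed. Larger counts would need a lower mean IQ than the conventional 100, for which the documents give no basis, and prior screening should remove some low scorers.

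Finally, section 3.1.1.2 says procedures will be fully explained, and all children receive the gift card. These features soften the burden but do not remove it. The general statement does not show that the gift-card condition is disclosed, and the stressor would still be given to a child who cannot enter the trial.

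**Conclusion.** The point holds in a limited form. As written, the plan allows a child without a diagnosed deficit who scores below 80 to complete the ECG, the stress test and the questionnaires before being excluded, and no earlier step can prevent it. The number is unknown: about 2 to 3 children if 3 to 5% of those reaching the session fail the cut, and about 6 at 9%, assuming that 60 are to be randomised and that there are no other losses.

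This is a matter of participant burden and procedural clarity. It leaves the planned power unchanged. It does not bias the comparison between arms so long as randomisation follows the eligibility decision, an order that section 4.2 implies but does not state.

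**What to change.** Amend section 2.4 to say that:

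- after consent and assent, the KBIT-2 is given and scored before any other study measure;
- the remaining measures, the ECG and the Trier Social Stress Test proceed only if the IQ criterion and all other eligibility criteria are met, and otherwise the session ends;
- the number of children screened out at this step is reported.

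Past-tense notes in sections 1.1 and 2.1 suggest that enrolment has already taken place. For children already assessed, the useful step is to report how many were excluded on the KBIT-2 and how many of those had completed the stress test.

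The cost is a few minutes of on-the-spot scoring and a short text change. No visit, instrument or participant is added, and assessment time is saved for each child who screens out.

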# **3.0 Consent Process and Documentation**

## **3.1 Consent Process**

### **3.1.1 Obtaining Informed Consent**

#### **3.1.1.1 Timing and Location of Consent**

Child will attend study assessment and treatment appointments at the TLC Clinic ([name]). The research assistant will obtain informed consent in a private setting/room

within the clinic when they attend the pre-treatment assessment session.

### **3.1.1.2 Coercion or Undue Influence during Consent**

Study procedures will be fully explained, voluntariness will be emphasized as well as the fact that declining participation will in no way impact the relationship of the participant with the TLC Clinic, Department of Pediatrics, or PSHMC.

### **3.1.2 Waiver or alteration of the informed consent requirement**

Waiver; recruitment of children.

A waiver of consent is requested to review medical record information to determine preliminary eligibility to participate in the research.

## **3.2 Consent Documentation**

### **3.2.1 Written Documentation of Consent**

The consent process will be documented in writing with the long form of consent documentation. The research assistant will assist in the explanation and obtaining of the written consent. A copy of the signed consent will be given to the participant and another copy will be saved in filing cabinets located at the TLC Clinic.

### **3.2.2 Waiver of Documentation of Consent (Implied consent, Verbal consent, etc.)**

A waiver of documentation of consent is requested for recruitment purposes because patients interested in the study will be calling the research assistant for a phone screening in response to seeing the recruitment letter or talking to staff at the CRC or TLC Clinic.

Verbal consent will be obtained from study therapists and dog handlers. A summary explanation of the research procedures will be provided to therapists and handlers about their role in completing the study. Verbal consent is used in this case as no PHI is collected from therapists or handlers.

### **3.3 Consent – Other Considerations**

#### **3.3.1 Non-English Speaking Subjects**

N/A: Excluded since the assessment materials used in the current study are only available in English, and have not been validated in other languages.

#### **3.3.2 Cognitively Impaired Adults**

##### **3.3.2.1 Capability of Providing Consent**

Caregivers with obvious cognitive, psychiatric, or other impairment that are incapable of understanding the purpose of the measures or participate in treatment will not be allowed to consent for themselves or their child.

##### **3.3.2.2 Adults Unable To Consent**

Adults unable to provide consent, and their children, will not be enrolled in this study. There would be concerns regarding their ability to provide informed consent and participate in treatment.

##### **3.3.2.3 Assent of Adults Unable to Consent**

N/A

#### **3.3.3 Subjects who are not yet adults (infants, children, teenagers)**

##### **3.3.3.1 Parental Permission**

All children in the study will be between the ages of 6 and 17 (inclusive). Each child will require the consent of a legal caregiver.

This will be obtained when they attend the scheduled pre-treatment assessment session at the TLC Clinic.

##### **3.3.3.2 Assent of subjects who are not yet adults**

Assent will be obtained from all youth participants and documented for all minors 7 years of age or older.

## 4.0 Study Design and Procedures

### 4.1 Study Design

Randomized clinical trial with two active conditions and no placebo or waitlist conditions.

### 4.2 Study Procedures

Children enrolled in the study will already demonstrate a sufficient elevation on the UCLA prior to completing the pre-treatment assessment, either at the TLC Clinic or the CRC. Additional measures (see below) will be completed at a pre-treatment session administered by the research assistant. Children will be randomly assigned to either the TF-CBT or TF-CBT+AAT condition using a blocked randomization procedure to balance the two groups on gender and age, thereby reducing bias and confounding that may be attributable to these factors (Efird, 2011). This randomization will be performed using a computer algorithm in SAS v. 9.4 with randomly selected block sizes of 4, 6, and 8. In addition, each child will be randomly assigned to one of two clinicians participating in the RCT using a random number generator. The randomization sequence will be defined prior to beginning the trial and will be developed and maintained by [name] (PSU Public Health Sciences). Children will be scheduled to complete a post-treatment assessment within 2 weeks of completing the 12th (final) session of the treatment protocol. The research assistant will administer the posttreatment assessment (measures described below) and all data collected will be entered into a database developed for this project using the Penn State College of Medicine's Research Electronic Data Capture (REDCap) system. Data monitoring and management, and statistical consultation, will be provided by [name]. The study will be single-blinded as all staff handling data will be blinded to a child's treatment condition (i.e., research assistants, [name], [name]). The study coordinator/research assistant will be responsible for reviewing study procedures with potential participants, liaising with the CRC, scheduling and verifying appointment times, conducting assessments, and contacting participants to re-schedule in the event that assessment sessions are missed.

The same two clinicians will implement the treatment in both conditions, thereby eliminating the impact of clinician-related factors on outcome. Both clinicians involved in the current project have completed requisite training and supervision requirements set forth by the TF-CBT developers and are certified TF-CBT clinicians. Clinicians will be required to complete and maintain a fidelity checklist (adapted from Deblinger et al., 2014; see attached) and the clinicians themselves will enter this data into REDCap to

ensure the research assistant remains blinded to participant condition. [name] will facilitate bi-weekly group TF-CBT supervision with the clinicians and be responsible for supervising research assistants.

The clinicians will be responsible for scheduling treatment sessions, which will occur once per week. This project will employ the standard TF-CBT treatment protocol, which includes twelve 90-minute sessions. TF-CBT is typically described as including 3 phases, each focusing on a common goal and encompassing a third of treatment (4 sessions). The first phase focuses on skills-building and includes psychoeducation, parenting skills training, relaxation skills training, affect modulation skills training, and cognitive coping skills training. The second phase involves focused gradual exposure activities, including construction of a narrative account of the child's maltreatment experiences and cognitive processing of maladaptive thoughts. The third phase emphasizes the child's mastery over environmental reminders of the maltreatment and includes sharing the trauma narrative with the caregiver, in vivo exposure to physical stimuli, and enhancing future development.

Susquehanna Service Dogs (SSD), a fully accredited member of Assistance Dogs International (ADI), will partner in the completion of this project (see letter of support from [name]). SSD facility dogs are fully trained/certified according to ADI standards and serve in canine-assisted interventions in local mental health settings. These dogs are skilled in basic obedience, maintain a calm manner and good social behavior in a variety of environments, and are trained for public access (<http://www.assistancedogsinternational.org/standards/assistance-dogs/standards-for-dogs/training-standards-for-facility-dogs/>). Three pre-determined facility dog/handler teams will participate in this project. Each team will schedule 4-hour blocks of time either in the morning or afternoon on various days of the week. Children assigned to the TF-CBT+AAT condition will be scheduled in one of these time blocks. The dog will then be considered an extension of the clinician; if the dog cannot attend an appointment then the appointment will be re-scheduled. This will assure that the child remains with the same dog each session for the duration of the protocol. Dogs will only be scheduled to participate with one child per day. If the child needs to change the regular appointment time, the dog's handler will be consulted and attempts will be made to re-schedule without changing the dog involved.

Having the dog's handler in the treatment room for the TF-CBT+AAT condition creates a significant confound as a second individual will not be present in the TF-CBT condition. Therefore, SSD handlers will deliver a 3-hour training to the clinicians in the management of the service dog and provide a further 7 hours of consultation to the clinicians throughout the project. When the session is ready to begin, the handler will transfer the handling duties to the clinician. Handlers will observe sessions through a

one-way mirror and/or closed circuit television system with a focus on monitoring the well-being of the dog. Handlers will be free to interrupt sessions if they believe it is warranted given the dog's behavior. Handlers will not be able to hear what is being discussed from the observation room, although various emotional responses will be visible and they may become aware of some details of the child's maltreatment. The clinicians will provide a 3-hour training to the handlers on secondary trauma and self-care, and provide continuing support to the handlers as needed.

Treatment sessions will be structured as follows: (1) A research assistant will facilitate the application of

electrodes to the child for purposes of recording psychophysiological data (see below). Research assistants will be trained to affix these electrodes by [name]. The dog's handler will affix a heart rate monitor to the dog as well as collect a saliva sample for cortisol analysis (see below; IACUC approval pending). [name] will train handlers in these procedures. Note data collection related to the dog is being performed by the handler in order to maintain the blinded status of the research assistant. (2) The child will be given 10 minutes of unstructured time prior to the implementation of treatment techniques to engage in relaxing, pleasurable activities while in the treatment room. Children in the TF-CBT group may select toys, games, books, or other activities, and children will be allowed to determine whether the clinician is involved in these activities. Children in the TF-CBT+AAT group will be given the same options; however, the dog will be in the room during these 10 minutes and the child may interact with the dog during that time. (3) The clinician will implement the child-focused TF-CBT components indicated for the given session (approximately 45 minutes). For the TF-CBT+AAT sessions, the dog will be instructed to sit or lay near the seated child during this time and the child will be allowed to pet or otherwise interact with the dog during the session. Children assigned to the TF-CBT group will be given the option of taking a stuffed animal or other tactile sensory stimulus (e.g., Koosh ball) into session. (4) The dog will be reunited with the handler, and the handler will remove the heart rate monitor from the dog and collect a saliva sample. Children in the TF-CBT+AAT group will be allowed to say good-bye to the dog. A research assistant then will facilitate the removal of electrodes from the child. (5) The clinician will implement the caregiver-focused TF-CBT components assigned for the given session (approximately 45 minutes) and a research assistant will implement indicated data collection procedures with the child (see below). The conditions specified in point (3) will apply during conjoint sessions where both the child and caregiver are present.

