#### **5.2 Sample size determination**

Although a primary objective of this study is to derive effect size estimates that can inform the design of a larger clinical trial, a preliminary power analysis was conducted. Results indicated that the proposed sample of 60 participants (equal sample sizes across the two conditions) can achieve 80% power to detect an approximately 5 point difference of pre-post change between the groups on the PTS measure (i.e., UCLA) when the standard deviation of each group is assumed to be 6.5 and the significance level is set at .05. Ethnic and gender composition will likely reflect those of the larger Harrisburg area (45% White, 45% African-American, 10% other ethnicities; 50% female, 50% male).

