## 5.2 Statistical methods

Intent-to-treat analyses will be used for all statistical analyses (i.e., all of the available data from randomized participants are utilized for analyses). Descriptive statistics (e.g., means, ranges, standard deviations) will be computed for continuous variables; frequencies will be calculated for

categorical variables. Measurements of PTS, emotional and behavioral concerns, and emotion regulation are continuous variables and will be examined over time with individual-level graphical checks. Transformation methods may be needed based on normality checks (i.e., Shapiro-Wilks test). To adjust for potential confounding variables that may be identified (e.g., gender, age, number of trauma types endorsed on the UCLA), multilevel models with partial nesting (i.e., youth in the TF-CBT+AAT group nested by dog, youth in the TF-CBT group not nested) will be employed to investigate the temporal trend and compare the trajectories of outcomes between the two groups using SAS PROC NL MIXED v. 9.4. Note that parameter estimates will be obtained using maximum likelihood estimation, and that p-values can be computed based on Chi-square tests (Liang & Zeger, 1986). If missing data or dropouts occur, the mechanism (i.e., missing completely at random, missing at random) will be explored and adjusted for valid statistical inference.

Analyses of categorical data (i.e., participant attrition, cancelled appointments, missed appointments without prior notice, and ability to implement TF-CBT techniques) will likely utilize descriptive and non-parametric methods (e.g., Fisher's exact tests). Differences between the conditions for treatment satisfaction will be examined with parametric (e.g., between groups t-tests) or non-parametric

analyses (Wilcoxon rank-sum tests). Given the small sample sizes and primary interest in a covariate effect, generalized estimating equations (GEE) can be used for the analysis of repeated cortisol assessments (Wang & Long, 2011). The GEE model with autoregressive (AR) working correlation structure can be fitted to investigate the difference of within session samples and between the treatment and control day samples. Three variables of interest are included: day of sample (0 = control; 1 = treatment), the session status (0 = pre-session; 1 = post-session; 2 = 20 minutes post-session), and their interaction.

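### Sharing two clinicians across arms does not eliminate clinician effects: no balancing of clinician within arm is described and no clinician term is pre-specified

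*Combined protocol and SAP*

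**What the plan says.** Section 4.2 (Study Procedures) makes the claim in one sentence: "The same two clinicians will implement the treatment in both conditions, thereby eliminating the impact of clinician-related factors on outcome".

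The same section describes two separate allocations. Arm is assigned "using a blocked randomization procedure to balance the two groups on gender and age", "with randomly selected block sizes of 4, 6, and 8". Clinician is then handled on its own: "each child will be randomly assigned to one of two clinicians participating in the RCT using a random number generator". The sequence is fixed before the trial starts, but blocking is described only for arm, and gender and age are the only balancing factors named.

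The Statistical methods section sets out a multilevel model with partial nesting: "youth in the TF-CBT+AAT group nested by dog, youth in the TF-CBT group not nested". It allows adjustment for confounders that may be found, with gender, age and number of trauma types as examples. Clinician does not appear anywhere in the statistical plan as a fixed effect, random effect or covariate.

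**The concern.** Each child is treated throughout by one of two people, so clinician is a plausible source of variation in outcome. Using the same pair in both arms prevents one clinician from being tied to one arm. It does not fix the share of each arm that each clinician treats, and it does not take clinician variation out of the residual. Those two things need balance in the allocation, a term in the model, or both, and the plan describes neither.

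At stake is the accuracy of the arm contrast in the one allocation that is realised. The Sample size determination section says that a primary objective is to obtain effect sizes for planning a larger trial, so the realised estimate will be carried forward. Gender and age are protected by blocking. Clinician is given weaker protection and a stronger claim.

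**Working it through.** **Inputs.** From the Sample size determination section: 60 children in equal arms, so 30 per arm; SD 6.5 per group; significance level 0.05 (two-sided assumed, as sidedness is not stated); a target of about 5 points in pre-post UCLA change. From section 4.2: two clinicians, assigned at random.

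**Assumptions, because the documents are silent.** The clinician draw is a simple, independent 50:50 draw. All 30 children per arm contribute. The two clinicians differ in mean UCLA change by 2, 3 or 5 points.

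**1. The plan's own figure.** The plan says the sample "can achieve 80% power to detect an approximately 5 point difference of pre-post change between the groups". The standard error of the contrast is 6.5 × √(2/30) = 1.68. The difference detectable with 80% power is 1.68 × (1.960 + 0.842) = 4.70 by the normal approximation, or 4.78 by the noncentral t. The stated figure is reproduced after rounding. At exactly 5 points, power is 84.6% (normal) or 83.4% (t).

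**2. Size of the imbalance.** Let A and B be one clinician's caseloads in the two arms, each Binomial(30, 0.5).
- SD of the difference in share: √(2 × 0.25/30) = 0.129, or 12.9 percentage points.
- P(|A − B| ≥ 4) = 0.366
- P(|A − B| ≥ 6) = 0.155
- P(|A − B| ≥ 8) = 0.052

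**3. Shift in the arm contrast.** Shift = (imbalance/30) × gap. The SD of the shift over allocations is 0.129 × gap.

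| Assumed gap | SD of shift | Shift, 6-child imbalance | As % of 5 points | In SE units (÷ 1.68) | Shift, 8-child imbalance |
|---|---|---|---|---|---|
| 2 | 0.26 | 0.4 | 8% | 0.24 | 0.53 |
| 3 | 0.39 | 0.6 | 12% | 0.36 | 0.80 |
| 5 | 0.65 | 1.0 | 20% | 0.60 | 1.33 |

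**4. Precision.** With an even split, the clinician share of variance is (gap²/4)/6.5².
- Gap 2: 1/42.25 = 2.4%
- Gap 3: 2.25/42.25 = 5.3%
- Gap 5: 6.25/42.25 = 14.8%

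If 6.5 already includes this variance, a clinician term lowers the residual SD to 6.42, 6.32 or 6.00, and power at 5 points rises from 83.4% to about 84%, 85% or 89% (t, ignoring the degree of freedom used). If 6.5 excludes it and no term is fitted, power is about 82.5%, 81.5% or 78.1%.

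**5. Type I error.** An unadjusted t-test was simulated under no arm effect. Over all allocations the error rate is about 5% at every assumed gap. Given an 8-child imbalance, it is about 5.7%, 6.7% or 10.5% for gaps of 2, 3 or 5 points.

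**The case against.** The main safeguards are in place. Clinicians are crossed with arm and children are randomised individually to them. Both clinicians are certified, receive joint supervision every two weeks, complete fidelity checklists and follow a standard 12-session protocol. A 5-point gap between two such clinicians would equal the whole target effect, so the top row of the table is an extreme case. Even there, a 6-child imbalance moves the estimate by 0.60 SE. All of this stands, and it keeps the point modest.

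Three stronger readings are tempting, and the documents do not support them.

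- **That the clinician draw is known to be unblocked.** The text mentions a random number generator and a pre-defined sequence. A pre-generated list can be restricted. What can be said is that no balancing of clinician within arm is described; the probabilities above hold only if the draw is simple.
- **That clinician differences will systematically appear as an effect of the dog.** Chance imbalance is as likely to favour TF-CBT as TF-CBT+AAT. Over allocations the contrast is unbiased.
- **That treating TF-CBT youth as not nested is a mis-specified cluster structure.** That phrase concerns dogs, which exist in one arm only, and it describes them correctly. Clinician is crossed with arm, and two levels are too few for a random effect.

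It can also be said that the covariate list is open, so a clinician term is not ruled out. That is true, but an open list does not secure the term. Adding it after the data are seen would be a discretionary choice.

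**Conclusion.** The concern holds in a limited form. The design removes confounding by clinician in expectation; it does not eliminate clinician effects in a single trial of 60, and the plan neither describes balance of clinician within arm nor pre-specifies adjustment.

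Under a simple 50:50 draw, there is roughly a one-in-six chance of an imbalance of 6 or more children. Its effect on the contrast is then at least 0.24 to 0.60 SE across the assumed gaps. The cost is conditional error in an unlucky allocation and some lost precision, about 2%, 5% or 15% of variance if the SD of 6.5 includes the gap. A reader might infer a threat to the validity of the comparison, but unbiasedness over allocations and overall type I error near 5% rule that out. The size rests on the assumed clinician gaps and on the assumed simple draw, neither of which the documents settle.

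The change is worth making because clinician is a factor the trial already randomises, and using it costs almost nothing.

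**What to change.** 1. In the existing pre-defined schedule, generate clinician assignment in permuted blocks within arm, so that each clinician treats about 30/2 = 15 children per arm. If the list is already restricted in this way, say so in section 4.2.
2. In the Statistical methods section, pre-specify clinician as a two-level fixed effect in the youth outcome models and keep the partial nesting by dog. Where the arm contrast is a difference in trajectory, include clinician by time as well, because the gap at issue is a gap in change.
3. In section 4.2, replace the claim of elimination with a statement that clinician is balanced across arms and adjusted for.

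The cost is one more column in the schedule, one degree of freedom in a model of change (with one more for each clinician-by-time term in a trajectory model) and one reworded sentence. No extra participants, staff or data are needed. If allocation has already started, the second change still applies, and the sentence should then claim adjustment, and claim balance only as far as the allocation achieved it.
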